Up to 250 current cigarette smokers will be recruited from the community surrounding Roanoke, VA. Eligible participants will be 18 to 65 years old, smoke at least 5 cigarettes per day, have a breath carbon monoxide (CO) level of at least 10 ppm at intake, and have no immediate plans to quit smoking. Females who are planning pregnancy, pregnant, lactating, not willing to use contraception during the study, and individuals who weigh less than 110 lbs or who have plans to move out of the area during the course of the experiment will be excluded from participation. Use of other tobacco/nicotine products will not be exclusionary. These minimally restrictive inclusion/exclusion criteria will allow for a broad range of participants and increase the generalizability to tobacco regulation of our eventual results. Individuals who do not meet these eligibility criteria may be rescreened to see if they are eligible after at least 30 days has passed.

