Seven Cigarette purchase sessions (approximately 1.5 hours). In the remaining seven cigarette purchase sessions (may be more than 7 due to factors outside of the control of participants, for example, a participant is eligible to start a purchase session but blood is unable to successfully be drawn), we will assess the behavioral economic demand intensity and elasticity of cigarettes with different nicotine concentrations. During each of these 7 cigarette purchase sessions, participants will consume either their usual brand of cigarette, an experimental cigarette containing 0.4 mg/g, 1.4 mg/g, 2.5 mg/g, 5.6 mg/g, or 17.4 mg/g nicotine, or a nonusual brand, commercially available cigarette. All but the nonusual brand, commercially available cigarettes will be presented in a randomized order across participants to control for any order effects; the nonusual brand, commercially available cigarette will be administered during the 7th session. The participants' preferred brand of conventional cigarettes will be used for the appropriate session. The cigarette doses will be blinded so the participants are not aware of the dose they will administer, leaving only subjective effects. Participants will be asked to abstain from consuming nicotine for 12 hours prior to each cigarette purchase session. Abstinence will be verified with breath CO at the beginning of the session, which will need to be <8 ppm to participate. If participants do not meet this criterion, they will be allowed to reschedule the session and try again. After repeated failed attempts, participant participation may be terminated. Each purchase session will begin with baseline ratings of nicotine craving, current drug effect, breath CO, and nicotine withdrawal symptoms. The baseline blood draw will also be collected at this time. Blood will be drawn with a catheter throughout the session by a registered nurse or other personnel with phlebotomist training to measure plasma nicotine levels during the sessions. The catheter will be removed at the end of each purchase session. Snacks and/or beverages will be available for the participants to consume, at their own discretion, should they begin to feel light-headed.

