Blood samples will be de-identified (i.e., only labeled with an arbitrary ID) and brought to or sent for testing to a laboratory that offers such services (e.g., LabCorp or Solstas at Carilion). Blood samples will only be tested for nicotine and the primary metabolite of nicotine (cotinine), after which they will be destroyed. In the event a researcher or other staff person is improperly exposed to a participant's blood, it will be tested for the presence of HIV, the Hepatitis B Virus, and the Hepatitis C Virus. The research team will follow proper procedures for testing and reporting as outlined by Virginia State Law, which includes sending the sample to a certified laboratory. Should a participant's blood require testing, s/he will be informed of the test results and provided with the opportunity to receive appropriate and timely counseling. In addition, the results will be sent to the local health department.

One Cigarette Comparison session (approx. 1.5 hours). After completing all blood draw sessions, participants may come back for one final in-lab session. No blood will be taken during this session. Participants will be provided an array of cigarettes consumed during the previous blood draw sessions. Cigarettes will be labeled with an arbitrary code (e.g., A, B, C) and participants may be told which of the blood draw sessions they consumed each cigarette. In the ventilated smoking booth, participants will take one to two puffs of each cigarette. Immediately after puffing the cigarette, participants will complete the tasks similar to those completed during the blood draw sessions (e.g., VAS ratings, hypothetical purchase tasks). Participants will take the one to two puffs approximately every 10 minutes and will be provided water or another bland beverage to cleanse the palate between puffs. After experiencing all cigarettes, participants will rank order the cigarettes (1-X [X being the number of cigarettes in the array] with 1 being the most preferred). Participants will also answer questions that directly compare each of the cigarettes (e.g., Assuming all of the cigarettes you just tried were available for you to purchase, would you pay to purchase and consume or would you pay to avoid and not consume this specific cigarette? And depending on their answer, What is the most you would pay to smoke 1 of these cigarettes OR What is the most you pay to avoid smoking 1 of these cigarettes).

5.2 DESCRIBE HOW DATA WILL BE COLLECTED AND RECORDED:

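### Experiment 1 checks 12-hour nicotine abstinence at session entry by breath CO alone, and the visible plan gives no rule for using the baseline plasma nicotine that could check it afterwards

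*Combined protocol and SAP*

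**What the plan says.** The Experiment 1 application, section 5.1 (cigarette purchase sessions), sets the requirement in terms of nicotine: "Participants will be asked to abstain from consuming nicotine for 12 hours prior to each cigarette purchase session". The verification follows directly: "Abstinence will be verified with breath CO at the beginning of the session, which will need to be <8 ppm to participate". On failure, "If participants do not meet this criterion, they will be allowed to reschedule the session and try again", and repeated failure may end participation.

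Section 3.1 of the same application states: "Use of other tobacco/nicotine products will not be exclusionary".

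Section 5.1 also provides for blood sampling at the start of each purchase session, alongside the craving, drug-effect, CO and withdrawal measures: "The baseline blood draw will also be collected at this time". The study cigarette follows five minutes into the session. On the assay: "Blood samples will only be tested for nicotine and the primary metabolite of nicotine (cotinine), after which they will be destroyed". Samples are "brought to or sent for testing to a laboratory that offers such services"; no same-day result is mentioned.

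The Data Analyses section for Experiment 1 plans mixed models of demand intensity, demand elasticity and VAS ratings by cigarette type, with a subject effect and, for demand, screened demographic covariates. It also plans analyses of demand against Cmax and AUC from the plasma nicotine curves. None of these mentions the baseline plasma value.

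**The concern.** The entry rule does not measure what the requirement asks for. A participant who also vapes, chews gum or uses snus could take nicotine shortly before a visit, meet the CO criterion and be recorded as abstinent.

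Two things are at stake. First, demand and VAS responses are meant to reflect the test cigarette in a deprived smoker. Nicotine taken beforehand could dull that response and shrink the contrasts between doses, including those at the low end where Aim 1 looks for its low-dose exception. Second, nicotine already in the blood adds to Cmax and AUC, and the visible plan describes no baseline correction. The addition is proportionally largest where the test cigarette delivers least.

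The baseline sample could reveal such sessions, but without a rule fixed in advance any later exclusion would be post hoc.

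**Working it through.** **1. Requirement against check**

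| Item | Where | Content |
|---|---|---|
| Requirement | Exp. 1, 5.1 | no nicotine from any source for 12 h |
| Entry check | Exp. 1, 5.1 | breath CO below 8 ppm |
| Population | Exp. 1, 3.1 | users of other tobacco or nicotine products eligible |
| Baseline sample | Exp. 1, 5.1 | plasma nicotine and cotinine, before the cigarette, every purchase session |
| Use of that sample to judge abstinence | Data Analyses, Exp. 1 | none stated |

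That CO marks smoke and not non-combusted nicotine is general knowledge and is not stated in the documents. Given that, rows 1 to 3 show that the entry check cannot verify the requirement for an eligible group. Rows 4 and 5 show that the means of checking later exists but is not assigned to that purpose.

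**2. The plan's power figure**

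Inputs from the Experiment 1 Sample Size Justification: n = 36 completers, m = 6 repeated measures, f = 0.175, alpha = 0.05, power 80%. The correlation between repeated measures (rho) and the sphericity correction are not given; I assume rho = 0.5 and epsilon = 1.

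- Noncentrality: lambda = f² × n × m / (1 − rho) = 0.030625 × 36 × 6 / 0.5 = 13.23
- Degrees of freedom: m − 1 = 5 and (n − 1)(m − 1) = 35 × 5 = 175
- Power from the noncentral F distribution: 0.7997

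The stated 80% reproduces, with no reserve. The result depends on rho: power is 0.461 at rho = 0, 0.632 at 0.3 and 0.965 at 0.7.

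**3. What dilution would cost (illustration only)**

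The documents give no rate of non-abstinent sessions. Suppose they shrink f by a fraction q, so that lambda = (0.175(1 − q))² × 432, where 432 = 36 × 6 / 0.5.

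| q | f | lambda | power, n = 36 |
|---|---|---|---|
| 0 | 0.175 | 13.23 | 0.800 |
| 5% | 0.166 | 11.94 | 0.751 |
| 10% | 0.1575 | 10.72 | 0.697 |
| 20% | 0.14 | 8.47 | 0.577 |

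Dropping affected completers altogether at f = 0.175 gives 0.772 with 34, 0.741 with 32 and 0.708 with 30. Excluding people therefore has its own cost, which favours flagging sessions in a sensitivity analysis.

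**4. Carry-over into Cmax and AUC**

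Write the observed exposure as the cigarette's contribution plus a carried-in amount c. The relative inflation is c divided by the cigarette's contribution. If absorbed nicotine were proportional to content (an assumption, for scale only), the same c would be a share 17.4 / 0.4 = 43.5 times larger for the 0.4 mg/g cigarette than for the 17.4 mg/g one. The size of c is unknown.

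**The case against.** **Nicotine use is measured at every session.** This stands. A reader might infer that vaping, gum or snus use goes undetected throughout the study. The documents do not support that: a pre-cigarette sample is taken at each purchase session and assayed for nicotine and cotinine. The gap is at entry, and in the absence of a rule for using the result.

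**The within-subject design blunts the bias.** This largely stands. Six of the seven conditions are in randomized order, so sporadic lapses should be unrelated to dose and mainly add noise. A stable habit that shifts all of a person's sessions equally is absorbed by the subject effect. Two limits remain: a subject effect removes a constant shift but not a flattened dose response, and the nonusual brand, fixed at session 7, lacks the protection of randomized order.

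**Part of the text is not visible.** The research-plan description of the purchase sessions resumes mid-sentence, and its session figure, Table 1 and the appendix are not shown. A time-of-last-use question may appear there, and missing text is not held against the plan. Section 5.1 of the application is complete on this step, however, and names only CO.

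**Lighter smokers.** Intake requires participants to "have a breath carbon monoxide (CO) level of at least 10 ppm at intake", only 2 ppm above the session limit, so a reader might infer that a light smoker could pass well short of 12 hours. That needs a CO half-life, which the documents do not give, and treats intake CO as the level when abstinence begins. I do not rely on it.

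**Conclusion.** The point holds in a limited form. The stated entry rule cannot verify abstinence from non-combusted nicotine in a population that may use it, and the visible plan does not say how the baseline plasma nicotine will be used to judge a session.

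The size is unknown. A reader might infer that the dose comparisons are contaminated or biased, or try to count the participants affected. The documents give neither the frequency of other-product use nor the rate of broken abstinence, and eligibility to use another product does not show use inside the 12-hour window. The likely consequences are diluted dose contrasts and some carry-over into Cmax and AUC, not systematic bias across the randomized conditions. The power figures are illustrations that rest on rho = 0.5, epsilon = 1 and proportional shrinkage of f.

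This is a cheap improvement, not a flaw that undermines the experiment.

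**What to change.** **Section 5.1, Experiment 1.** At the start of each purchase session, record the time of last use of every nicotine product, including e-cigarettes, gum, snus and other smokeless products. Apply the existing reschedule rule to reported use inside the 12-hour window already stated. Keep the CO check.

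**Data Analyses, Experiment 1.** Before the data are seen, specify an absolute baseline plasma nicotine threshold above which a session is flagged as inconsistent with abstinence, and justify the value. A comparison with the participant's own other sessions may be added but is not enough alone, because it misses someone who uses nicotine before every visit. Repeat the demand, VAS and plasma nicotine models either without flagged sessions or with baseline nicotine as a session-level covariate, and report the number of flagged sessions by cigarette type.

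**Cost.** One question per session, slightly more rescheduling among dual users, and one sensitivity analysis. No new sample, assay or participant is needed. The question relies on self-report, so the plasma flag is the objective check; with no same-day result stated, it works only in retrospect.

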7.1 DOES THE RESEARCH INVOLVE MICROWAVES/X-RAYS, OR GENERAL ANESTHESIA OR SEDATION?

- No
- Yes

7.2 DO RESEARCH ACTIVITIES INVOLVE PRISONERS, PREGNANT WOMEN, FETUSES, HUMAN IN VITRO FERTILIZATION, OR MENTALLY DISABLED PERSONS?

- No, go to question 7.3
- Yes, answer questions within table

IF YES

This research involves:

Prisoners
 Pregnant women Fetuses Human in vitro fertilization
 Mentally disabled persons

7.3 DOES THIS STUDY INVOLVE MORE THAN MINIMAL RISK TO STUDY PARTICIPANTS?

Minimal risk means that the probability and magnitude of harm or discomfort anticipated in the research are not greater in and of themselves than those ordinarily encountered in daily activities or during the performance of routine physical or psychological examinations or tests. Examples of research involving greater than minimal risk include collecting data about abuse or illegal activities. Note: if the project qualifies for Exempt review (<http://www.irb.vt.edu/pages/categories.htm>), it will not need to go to the Full Board.

No
 Yes

IF YOU ANSWERED “YES” TO ANY ONE OF THE ABOVE QUESTIONS, 7.1, 7.2, OR 7.3, THE BOARD MAY REVIEW THE PROJECT’S APPLICATION MATERIALS AT ITS MONTHLY MEETING. VIEW THE FOLLOWING LINK FOR DEADLINES AND ADDITIONAL INFORMATION: <http://www.irb.vt.edu/pages/deadlines.htm>

Section 8: Confidentiality / Anonymity

For more information about confidentiality and anonymity visit the following link: <http://www.irb.vt.edu/pages/confidentiality.htm>

8.1 WILL PERSONALLY IDENTIFYING STUDY RESULTS OR DATA BE RELEASED TO ANYONE OUTSIDE OF THE RESEARCH TEAM?

For example – to the funding agency or outside data analyst, or participants identified in publications with individual consent

No
 Yes, to whom will identifying data be released? **Participant's identifying information (e.g., name, address, phone number) may be released to the FBRI at VTC administrative offices and the VT Controller's office in order to process the petty cash reimbursements for participant payments.**

8.2 WILL ANY STUDY FILES CONTAIN PARTICIPANT IDENTIFYING INFORMATION (E.G., NAME, CONTACT INFORMATION, VIDEO/AUDIO RECORDINGS)?

Note: if collecting signatures on a consent form, select “Yes.”

No, go to question 8.3

Yes, answer questions within table

IF YES

Describe if/how the study will utilize study codes: Using only ID numbers and initials and keeping all data in locked offices will protect confidentiality. Computer databases will have coded identifiers and all computers will be password protected.

If applicable, where will the key [i.e., linked code and identifying information document (for instance, John Doe = study ID 001)] be stored and who will have access? Master files linking subject names to study ID numbers will be accessible only to trained study team members delegated this access by the PI.

Note: the key should be stored separately from subjects' completed data documents and accessibility should be limited.

The IRB strongly suggests and may require that all data documents (e.g., questionnaire responses, interview

responses, etc.) do not include or request identifying information (e.g., name, contact information, etc.) from participants. If you need to link subjects' identifying information to subjects' data documents, use a study ID/code on all data documents.

8.3 WHERE WILL DATA BE STORED?

Examples of data - questionnaire, interview responses, downloaded online survey data, observation recordings, biological samples

All data and participant binders will be stored in a safe place to protect confidential participant information. Safe places will include locked filing cabinets or locked rooms accessible only to study personnel. The full names of participants will not be listed on the outside of binders to protect confidentiality of study participants.

Electronic data will be saved in secure, limited access shared drives on password-protected computers accessible only to the research team.

8.4 WHO WILL HAVE ACCESS TO STUDY DATA?

Access to study data will be limited to study personnel who have completed the Virginia Tech IRB Human Subjects Tutorial and who have been delegated the responsibilities of data collection, management, or analyses by the PI.

8.5 DESCRIBE THE PLANS FOR RETAINING OR DESTROYING THE STUDY DATA

Data collected from this study will be retained and destroyed in accordance with the center's policy that requires a 3-year retention period following final publication of the data.

8.6 DOES THIS STUDY REQUEST INFORMATION FROM PARTICIPANTS REGARDING ILLEGAL BEHAVIOR?

No, go to question 9.1

Yes, answer questions within table

IF YES

Does the study plan to obtain a Certificate of Confidentiality?

No

Yes (Note: participants must be fully informed of the conditions of the Certificate of Confidentiality within the consent process and form)

*For more information about Certificates of Confidentiality, visit the following link:
<http://www.irb.vt.edu/pages/coc.htm>*

Section 9: Compensation

For more information about compensating subjects, visit the following link: <http://www.irb.vt.edu/pages/compensation.htm>

9.1 WILL SUBJECTS BE COMPENSATED FOR THEIR PARTICIPATION?

No, go to question 10.1

Yes, answer questions within table

IF YES

What is the amount of compensation? Compensation for participation will be as follows:

\$20.00 for completion of informed consent

\$40.00 for the assessment session

\$40.00 for each of the completed cigarette purchase session (7 total)

\$20.00 for the cigarette comparison session

\$75.00 bonus for completing all sessions

\$10 for cigarette purchase sessions that are discontinued due to situations outside of the control of participants (i.e. a participant is eligible to begin a cigarette purchase session, but the session is discontinued due to an inability to successfully draw blood)

Combined, the subjects could be compensated approximately \$435 by completing all aspects of the experiment.

To allow for payments that are both convenient and rapidly available, we may pay participants with reloadable prepaid cards through Greenphire ClinCard (www.greenphire.com), an FDIC-insured payment provider that specializes in clinical trial stipend payments that comply with IRB privacy regulations and considerations. At the beginning of the study, the participant will receive a prepaid MasterCard debit card that can be used anywhere that accepts MasterCard. As payments are earned in the course of the study, additional funds will be added to the account for that participant. Funds are immediately available when added and participants can check their balance as desired. This system will allow frequent, immediately available payments. Payments may also be made via check, however remote debit card payments will be used most often.

Will compensation be prorated?

Yes, please describe: **Subjects will be compensated based on what study procedures he/she has completed.**

No, explain why and clarify whether subjects will receive full compensation if they withdraw from the study?

Unless justified by the researcher, compensation should be prorated based on duration of study participation. Payment must not be contingent upon completion of study procedures. In other words, even if the subject decides to withdraw from the study, he/she should be compensated, at least partially, based on what study procedures he/she has completed.

Section 10: Audio / Video Recording

For more information about audio/video recording participants, visit the following link: <http://www.irb.vt.edu/pages/recordings.htm>

10.1 WILL YOUR STUDY INVOLVE VIDEO AND/OR AUDIO RECORDING?

No, go to question 11.1

Yes, answer questions within table

IF YES

This project involves:

Audio recordings only

Video recordings only

Both video and audio recordings

Provide compelling justification for the use of audio/video recording:

How will data within the recordings be retrieved / transcribed?

How and where will recordings (e.g., tapes, digital data, data backups) be stored to ensure security?

Who will have access to the recordings?

Who will transcribe the recordings?

When will the recordings be erased / destroyed?

Section 11: Research Involving Students

11.1 DOES THIS PROJECT INCLUDE STUDENTS AS PARTICIPANTS?

No, go to question 12.1

Yes, answer questions within table

IF YES

Does this study involve conducting research with students of the researcher?

No

Yes, describe safeguards the study will implement to protect against coercion or undue influence for participation:

Note: if it is feasible to use students from a class of students not under the instruction of the researcher, the IRB recommends and may require doing so.

Will the study need to access student records (e.g., SAT, GPA, or GRE scores)?

No

Yes

11.2 DOES THIS PROJECT INCLUDE ELEMENTARY, JUNIOR, OR HIGH SCHOOL STUDENTS?

No, go to question 11.3

Yes, answer questions within table

IF YES

Will study procedures be completed during school hours?

No

Yes

If yes,

Students not included in the study may view other students' involvement with the research during school time as unfair. Address this issue and how the study will reduce this outcome:

Missing out on regular class time or seeing other students participate may influence a student's decision to participate. Address how the study will reduce this outcome:

Is the school's approval letter(s) attached to this submission?

Yes

No, project involves Montgomery County Public Schools (MCPS)

No, explain why:

You will need to obtain school approval (if involving MCPS, click here: <http://www.irb.vt.edu/pages/mcps.htm>). Approval is typically granted by the superintendent, principal, and classroom teacher (in that order). Approval by an individual teacher is insufficient. School approval, in the form of a letter or a memorandum should accompany the approval request to the IRB.

